STUDY SYNOPSIS

Study Title	A pre-market, multi-center, international, open-label, single-arm study to evaluate the safety and performance of a Class III medical device (GreenBone Implant) for surgical repair of long bone defects
Study Code	GB-02-18
Study Sponsor	GreenBone Ortho S.r.l. [name] – Italy
Clinical Phase	Pre-market clinical investigation of a Class III Investigational Medical Device.
Study Design	Multi-center, international, prospective, open-label, single-arm, first-in-human clinical investigation. The Patients enrolled in this clinical investigation will undergo a scheduled surgery for the treatment of long bone defects up to 6 cm using GreenBone Implant. After the surgery, the Patients will be monitored at pre-scheduled visits up to 12 months. Adverse events, pain, quality of life and functional parameters, as well as X-ray and CT scan, will be evaluated at scheduled follow-up visits. An independent DSMB will review the safety reports at regular intervals and Serious Adverse Events (SAE) as soon as reported, to protect Patients participating in the study. The initial phase of the study contemplates the treatment of bone defects up to 3 cm. An adaptive interim analysis will be performed when the first 7 Patients will have completed the 6-month follow-up visit. The DSMB will review the results of the interim analysis with respect to the primary endpoint (safety), and provide one of the following recommendations to the Sponsor: a) to stop the study for unacceptable frequency and severity of adverse events or b) to continue the study up to 25 Patients recruited and to include at least 5 Patients with a longer bone defect (> 3 cm up to 6 cm).
Investigational Medical Device	GreenBone Implant for bone substitution, a Class III Medical Device. The GreenBone Implant had not yet received the CE mark at the time of the Study first submissions and first patient enrollment. The Device received the CE mark in December 2019.
Investigational Medical Device Use	GreenBone Implant is used in the surgical procedures for repair of bones defects.
Investigational Medical Device Description	GreenBone Implant is a ceramic reabsorbable scaffold with a geometrical structure, engineered to reflect anatomical and physiological bone hierarchical structures. GreenBone Implant scaffold is made of biomimetic substituted calcium phosphate phases (HA and β -TCP and minerals). It is suitable for repair of defects in bones. GreenBone Implant is a EU class III Medical Device.

Clinical Investigation Rationale	
Bone defects can result from malformation, high-energy traumatic events, bone resection due to different pathologies such as tumors or infections, or from the treatment of complex non-unions, all very challenging conditions in orthopedic practice.
 
Current treatment of bone defects usually implies the use of bone grafts and/or biocompatible materials, to create a scaffold that bridges the defect, favoring the migration of cells from the neighboring tissues to fill the gap. Autograft and Allograft are the treatments most currently used for large bone loss, but both treatments have significant disadvantages. Different types of synthetic materials have been tested for repair of long bone gaps.
 
However, at the moment, there is not any bone substitute with the ideal/desirable osteoinductive, osteoconductive and mechanical properties. GreenBone Implant is a synthetic, acellular, reabsorbable, new generation bone graft, being suitable for surgical reconstruction of bone defects.

Study Objectives	
The primary objective of this study is to assess the safety profile of the GreenBone Implant in Patients undergoing surgery for the treatment of bone defects up to 6 cm, specifically for long bone repair. The initial phase of the study contemplates the treatment of bone defects up to 3 cm. Following DSMB interim assessment, at least 5 Patients, of the 25 patients, with a longer bone defect (> 3 up to 6 cm) will be enrolled.
 
The secondary objectives of this study are:
 
- To evaluate the progression of bone healing and bone regeneration at the level of the intervention site after use of GreenBone Implant throughout a 12-month observation period;- To evaluate the degree of pain throughout a 12-month observation period;- To evaluate the functional recovery of Patient throughout a 12-month observation period.- To evaluate the health related quality of life of Patient throughout a 12-month observation period.
Implant of the Investigational Medical Device	
GreenBone Implant is applied to the bone gap by the surgeon during the scheduled intervention, according to standard clinical practice and to the information provided by GreenBone Ortho S.r.l. in the device Instructions For Use (IFU) document.

Study Population	
Male and female Patients, aged between 18 and 65 years, undergoing surgery for the treatment of long bone defects up to 6 cm.
 
Please note: The initial phase of the study contemplates the treatment of bone defects up to 3 cm. After an adaptive interim analysis review by the DSMB, inclusion criteria will be amended; specifically to include the recruitment of patients suffering from bone defects up to 6 cm.

Study Sample Size	In the absence of published guidance on first-in-human trials on long bone surgery, the sample size (n=25 including a 20% drop-out rate) has been chosen to be consistent with first-in-human studies of pharmacological agents which are usually conducted in 10-15 patients (Rubinstein LV et al 2010).
Inclusion Criteria	
1. Male or female Patients.2. Patients aged ≥ 18 and ≤ 65 years old.3. Patients requiring long bone defect reconstructions up to 3 cm, resulting from high-energy traumatic events, or from the treatment of complex bone non-unions in the extremities (arms and legs), or patients undergoing the second stage of the Masquelet technique.4. Patients understanding the nature of the study and providing their informed consent to participation.5. Patients willing and able to attend the follow-up visits and procedures foreseen by study protocol. 
Please note: after interim analysis review by the DSMB, inclusion criteria n. 3 will be modified as follows (all Investigators will be notified by the Sponsor, and adequate training by CRA will be conducted):
 
Change of inclusion criteria n. 3: Patients requiring long bone defect reconstructions up to 6 cm, resulting from high-energy traumatic events, or from the treatment of complex bone non-unions in the extremities (arms and legs), or patients undergoing the second stage of the Masquelet technique.

Exclusion Criteria	
For the specific characteristics of this study, the final decision on Patient enrolment will be made by the Investigator at time of surgery (during surgery, before implantation).
 
1. Patients with bone infection at the time of enrolment.2. Patients with bone malignant tumor(s) at the time of enrolment.3. Patients who have been treated with chemotherapy or radiotherapy within 12 months before the enrolment.4. Patients with concomitant infectious systemic diseases at the time of enrolment.5. Patients with known inflammatory systemic diseases at the time of enrolment.6. Patients with concomitant myeloproliferative disorders at the time of enrolment.7. Patients currently treated with systemic immunosuppressive agents, excluding steroids.8. Patients with active autoimmune disease.9. Patients with a pre-existing calcium metabolism disorder (i.e. hypercalcemia).10. Known hyperthyroidism or autonomous thyroid adenoma.11. Patients with coagulopathy or bleeding disorders.

	
12. Patients who are not allowed to undergo the study procedures involving imaging (X-rays, CT scan) based on Investigator's judgement.
 
13. Patients with known or suspected allergy or hypersensitivity to the GreenBone Implant components.
 
14. Patients who are participating or have participated in other clinical studies within the 30 days before the study enrolment.
 
15. Patients identified by the Investigator to have intra-operative findings that may preclude conduct of study procedure.
 
16. Patients with occurrence of major intra-operative complications that require resuscitation or deviation from the planned surgical procedure.
 
17. Women who are pregnant or breast-feeding or who wish to become pregnant during the period of the clinical investigation and for three months later.
 
18. Female Patients of childbearing age (less than 24 months after the last menstrual cycle) who do not use adequate contraception *.
						
	
* Methods at low risk of contraceptive failure (less than 1% per year) when used consistently, including: combined (estrogen and progestogen containing) hormonal contraception associated with inhibition of ovulation (oral, intravaginal, transdermal), progestogen-only hormonal contraception associated with inhibition of ovulation (oral, injectable, implantable), some intra-uterine devices.
 
Please note: exclusion criteria after interim analysis will remain the same.
						
Not Allowed Concomitant Medications	Systemic immunosuppressive agents, excluding steroids.						
Study Flow Chart	
  
 Visit	Procedures	Day	
   
 Visit 1 (V1 – Screening)	 
 • Eligibility criteria evaluation • Demography / medical history • Informed consent collection • Patient enrolment • Standard preoperative lab assessment • Vital signs • Physical examination • ECG • X-Ray examination • CT scan examination (if necessary) • Quality of Life (EuroQoL EQ-5D-5L Validated Questionnaire) • VAS score (0-10 point scale) • Functional assessment (36-Item Short Form Survey – SF-36) • Concomitant medications • Pregnancy test (for female Patients of childbearing age) 	Up to 7 days before V2	
  
	Visit	Procedures	Day	Visit 1 (V1 – Screening)	
 • Eligibility criteria evaluation • Demography / medical history • Informed consent collection • Patient enrolment • Standard preoperative lab assessment • Vital signs • Physical examination • ECG • X-Ray examination • CT scan examination (if necessary) • Quality of Life (EuroQoL EQ-5D-5L Validated Questionnaire) • VAS score (0-10 point scale) • Functional assessment (36-Item Short Form Survey – SF-36) • Concomitant medications • Pregnancy test (for female Patients of childbearing age) 	Up to 7 days before V2
Visit	Procedures	Day					
Visit 1 (V1 – Screening)	
 • Eligibility criteria evaluation • Demography / medical history • Informed consent collection • Patient enrolment • Standard preoperative lab assessment • Vital signs • Physical examination • ECG • X-Ray examination • CT scan examination (if necessary) • Quality of Life (EuroQoL EQ-5D-5L Validated Questionnaire) • VAS score (0-10 point scale) • Functional assessment (36-Item Short Form Survey – SF-36) • Concomitant medications • Pregnancy test (for female Patients of childbearing age) 	Up to 7 days before V2					

	
Visit 2 (V2 – Surgery)
	
Before surgery:
 
 • Informed Consent confirmation by the Patient 
During and after surgery:
 
 • Device implantation: application of the GreenBone Implant at the target site • Evaluation of technical success • Concomitant medications • Adverse events • Provide Implant Card to each patient • Return of discarded devices (if any) and completion of the report of Investigational Medical Device Deficiency 	D 0
	
Visit 3 (V3 – Control 1)
	
 • Physical examination of the operated limb • X-Ray examination • Evaluation of global tolerability of Patient (by the Investigator) • Quality of Life (EuroQoL EQ-5D-5L Validated Questionnaire) • VAS score (0-10 point scale) • Functional assessment (36-Item Short Form Survey – SF-36) • Concomitant medications • Adverse events 	D +30 ±3 (1M)
	
Visit 4 (V4 – Control 2)
	
 • Physical examination of the operated limb • X-Ray examination • Evaluation of global tolerability of Patient (by the Investigator) • Quality of Life (EuroQoL EQ-5D-5L Validated Questionnaire) • VAS score (0-10 point scale) • Functional assessment (36-Item Short Form Survey – SF-36) • Concomitant medications • Adverse events 	D +60 ±5 (2M)

	Visit 5 (V5 – Control 3)	
 Physical examination of the operated limb X-Ray examination Evaluation of global tolerability of Patient (by the Investigator) Quality of Life (EuroQoL EQ-5D-5L Validated Questionnaire) VAS score (0-10 point scale) Functional assessment (36-Item Short Form Survey – SF-36) Concomitant medications Adverse events 	D +90 ±7 (3M)
	Visit 6 (V6 – Control 4)	
 X-Ray examination CT scan examination (if healing activity inconclusive on radiographs) Evaluation of global tolerability of Patient (by the Investigator) Quality of Life (EuroQoL EQ-5D-5L Validated Questionnaire) VAS score (0-10 point scale) Functional assessment (36-Item Short Form Survey – SF-36) Concomitant medications Adverse events 	D +180 ±14 (6M)
	Visit 7 (V7 – Control 5)	
 X-Ray examination Evaluation of global tolerability of Patient (by the Investigator) Quality of Life (EuroQoL EQ-5D-5L Validated Questionnaire) VAS score (0-10 point scale) Functional assessment (36-Item Short Form Survey – SF-36) Concomitant medications Adverse events 	D +270 ±14 (9M)
	Visit 8 (V8 – Control 6)	
 X-Ray examination CT scan examination (if healing activity inconclusive on radiographs) Evaluation of global tolerability of Patient (by the Investigator) Quality of Life (EuroQoL EQ-5D-5L Validated Questionnaire) VAS score (0-10 point scale) Functional assessment (36-Item Short Form Survey – SF-36) Concomitant medications Adverse events 	D +360 ±14 (12M)

	Should any of the Patients request at any time an additional visit (i.e. in case of discomfort in the area of intervention), an additional visit should be organized to allow examination by the Investigator.
Study Endpoints	
Primary Endpoint:
 
Evaluation of adverse events rate during the study period. All adverse occurrences (serious/non-serious or device-related/non device-related) will be recorded prospectively, categorized and evaluated for causality using defined criteria.
 
The study will be monitored by an independent Data Safety Monitoring Board (DSMB).

Study Endpoints	
Secondary Endpoints:
 
1. Evaluation of technical success, defined as successful delivery of the GreenBone Implant in the target defect bone evaluated at V2 (during surgical procedure).2. Evaluation of the bone regeneration in the area of intervention in comparison to baseline (V1), by means of X-ray examination, on visits V3, V4, V5, V6, V7 and V8. X-ray scoring systems have been implemented according to the criteria proposed by Lane and Sandhu (bone formation, union and remodeling) (Lane 1987) (See Appendix 1).3. Evaluation of the bone regeneration in the area of intervention in comparison to baseline (V1), by means of CT scan examination on visits V6 and V8 if indicated.4. Functional Assessment: evaluation of functional recovery of Patient, by means of a standardized questionnaire (36-Item Short Form Survey – SF-36), on visits V1, V3, V4, V5, V6, V7 and V8 (See Appendix 2).5. Evaluation of degree of pain perceived by the Patient, by means of a VAS (0-10 point scale), on visits V1, V3, V4, V5, V6, V7 and V8 (Price 1983) (See Appendix 3).6. Evaluation of Quality-of-Life by means of EuroQoL EQ-5D-5L Validated Questionnaire, on visits V1, V3, V4, V5, V6, V7 and V8 (See Appendix 4).7. Evaluation of global tolerability to treatment of Patient (by the Investigator), through a standardized questionnaire, on visits V3, V4, V5, V6, V7 and V8 (See Appendix 5).8. Evaluation of the number of re-interventions occurring for the Patient throughout the 12-month observation period.

Statistical Analysis	
A descriptive analysis of safety and performance variables will be performed.
 
The descriptive analyses will be performed in order to describe the nature of adverse events, their distribution and frequency. Moreover, all factors which may appear predictive for the rate of adverse events will be analyzed (age, sex, dimension of the implanted device, system used, diabetes history, smoking habits, alcohol consumption, concomitant treatments/diseases, other). If the percentage of Patients with device-related AE would be sufficiently large in respect to the overall sample ($\geq 70\%$) to allow an evaluation of the time interval between the date of surgery and the date of the first adverse event occurrence, a median of the time interval will be estimated, with 95% Confidence Interval, through the Kaplan-Meier survival analysis.
 
An adaptive interim analysis will be performed when the first 7 Patients will have completed the 6-month follow-up visit. An independent Data Safety Monitoring Board (DSMB) will review the results of the interim analysis with respect to the primary endpoint (safety), and provide one of the following recommendations to the Sponsor: a) to stop the study for unacceptable frequency and severity of adverse events or b) to continue the study up to a minimum of 25 Patients recruited and to include at least 5 Patients with a longer bone defect (> 3 up to 6 cm).
 
The independent DSMB will receive all the safety data at regular intervals and the data about Serious Adverse Events (SAE) as soon as reported, to protect Patients participating in the study.

Investigational Sites	The study will involve 8 investigational sites in Bosnia & Herzegovina, Israel, Italy, Serbia, Slovenia, Switzerland and UK.

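### The interim review that precedes opening the study to defects over 3 cm and up to 6 cm is tied to adverse events; the plan does not send the DSMB the 6-month imaging of the first 7 implants

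*Combined protocol and SAP*

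**What the plan says.** All references are to the Study Synopsis in the combined protocol and SAP.

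- **Trigger (Study Design; Statistical Analysis).** "An adaptive interim analysis will be performed when the first 7 Patients will have completed the 6-month follow-up visit". The initial phase covers defects up to 3 cm, so these 7 patients are at or below that length.
- **Scope of the review.** The Study Design row says "The DSMB will review the results of the interim analysis with respect to the primary endpoint (safety", and the Statistical Analysis row repeats the limit: "An independent Data Safety Monitoring Board (DSMB) will review the results of the interim analysis with respect to the primary endpoint (safety". The Primary Endpoint entry defines this endpoint as the adverse event rate. It covers all adverse occurrences, whether or not serious or device-related.
- **Listed recommendations (Study Design).** There are two: "a) to stop the study for unacceptable frequency and severity of adverse events", or "to continue the study up to 25 Patients recruited and to include at least 5 Patients with a longer bone defect" (over 3 cm and up to 6 cm).
- **Consequence (Study Population; Inclusion Criteria).** After this review, criterion 3 widens from 3 cm to 6 cm. No further condition is given.
- **Healing data (Secondary Endpoints 2 and 3; Study Flow Chart).** Bone regeneration is scored on X-ray at V3 to V8. CT is done at V6 and V8 only when needed: "CT scan examination (if healing activity inconclusive on radiographs".
- **Re-interventions (Secondary Endpoint 8).** "Evaluation of the number of re-interventions occurring for the Patient throughout the 12-month observation period".
- **Other data reaching the DSMB (Study Design; Statistical Analysis).** Safety reports or safety data at regular intervals, and serious adverse events as they are reported.

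**The concern.** The implant is a resorbable scaffold meant to be replaced by bone across a gap, and the interim review precedes a doubling of the maximum gap from 3 cm to 6 cm. Whether the shorter gaps are filling is directly relevant to that step. The plan collects this information on the right timescale but places it in secondary endpoints, outside the stated scope of the review.

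A patient whose films show little progress at 6 months, but who has no recorded adverse event, would add nothing to the review as described. The DSMB could recommend including longer defects on a reassuring adverse event table while the images of the same patients point the other way. At least 5 patients with longer defects would then be enrolled in a first-in-human study without the most relevant available evidence having been weighed.

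**Working it through.** The plan gives no healing rate, adverse event threshold, alpha or power for this decision, so there is no stated figure to reproduce. The check has two parts: comparing entries, and a binomial illustration.

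**1. What is due by the trigger, and whether it reaches the DSMB**

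| Information on the first 7 patients | Due by the 6-month visit? | Stated route to the DSMB |
|---|---|---|
| Adverse events, including serious ones | Yes | Interim review and regular safety reporting |
| Device deficiencies | Yes (V2) | Not named; probably through safety reporting |
| Events leading to re-intervention | Yes, if they have occurred | Not named; probably as adverse events |
| X-ray scores at V3 to V6 (days 30, 60, 90, 180) | Yes, as scheduled | None stated |
| CT at V6, where radiographs are inconclusive | Yes, if done | None stated |

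The last two rows are the gap. The listing would be small: 7 patients × 4 scheduled X-rays = 28 films, plus any V6 CT.

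**2. Whether an adverse event record would carry the same information**

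The primary endpoint is broad enough that non-union might be recorded as an adverse event. The text does not say that it must be. Criterion 3 admits patients being treated for complex non-unions, so persistent non-healing could also be read as the pre-existing condition. Capture through adverse events is possible but not assured.

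**3. Whether 7 patients can show anything useful**

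Let p be the true proportion with healing failure at 6 months. The documents give no value, so a range is assumed. With 7 independent patients, all with readable films:

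- P(at least 1) = 1 − (1 − p)^7
- P(at least 2) = 1 − (1 − p)^7 − 7p(1 − p)^6

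| Assumed p | P(at least 1 of 7) | P(at least 2 of 7) |
|---|---|---|
| 10% | 1 − 0.478 = 52% | 1 − 0.478 − 0.372 = 15% |
| 20% | 1 − 0.210 = 79% | 1 − 0.210 − 0.367 = 42% |
| 30% | 1 − 0.082 = 92% | 1 − 0.082 − 0.247 = 67% |
| 40% | 1 − 0.028 = 97% | 1 − 0.028 − 0.131 = 84% |

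A moderate or high failure rate would probably show in the films; a low one might not. The converse is weak. With 0 of 7 failures, the exact two-sided 95% upper limit is 1 − 0.025^(1/7) = 41.0%. The imaging can raise a warning but cannot establish that healing is satisfactory.

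**4. Whether adding the listing would be enough**

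It would not. The recommendations are to stop for adverse events, or to continue and include longer defects. A DSMB that saw poor healing and a clean adverse event table would find no listed recommendation to match.

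**The case against.** The best defence is that safety is the primary objective, so gating a first-in-human extension on safety is a coherent choice. The text is a synopsis: it contains no DSMB charter and no full set of adverse event definitions, and events are to be evaluated by criteria not set out here. A charter may already put the films before the DSMB. This stands in part. It lowers confidence, but it does not alter the scope that the synopsis states twice, or the wording of the two recommendations.

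Three stronger readings are tempting and are not supported:

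- **That the DSMB is barred from seeing healing data.** Nothing forbids it. The text simply does not require it.
- **That re-interventions and delivery problems are hidden from the DSMB.** Making re-intervention a secondary endpoint does not remove the underlying events from adverse event reporting. V2 also records adverse events and device deficiencies alongside technical success.
- **That absence of union at 6 months means the implant has failed.** Healing is followed to 12 months, with X-rays at V7 and V8 and conditional CT at V8. No 6-month union threshold is set. A 6-month image is supporting information, not a final outcome.

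It is also fair to say that 7 patients give little precision. That limits what the imaging can prove. It is no reason to leave out data already collected.

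**Conclusion.** The point holds as a gap in what the interim review is stated to cover. As written, the recommendation that precedes opening the study to longer defects rests on adverse events, and radiographic healing of the first 7 implants has no stated route into it. A reader might go further and infer that patients with longer defects will be enrolled despite known healing failure. The documents do not show this: non-union might be logged as an adverse event, and the DSMB could ask for the films.

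The size can only be illustrated. Across assumed failure rates of 10% to 40%, the chance that the films show at least one failure runs from 52% to 97%, and at least two from 15% to 84%. No rate in that range comes from the documents. The figures assume independent patients and complete, readable films; visits are scheduled, but completion of every film is not guaranteed.

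This is a cheap improvement. Confidence is medium, because a charter or adverse event definitions outside the available text could close part of the gap.

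**What to change.** In the Study Design and Statistical Analysis rows:

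1. State that the interim package contains adverse events plus a per-patient listing of V3 to V6 X-ray scores, any V6 CT, re-interventions, device deficiencies and defect length.
2. State that the DSMB considers all of these in its recommendation on defects over 3 cm and up to 6 cm.
3. Reconcile the two listed recommendations with this wider review, so that the healing data can affect the outcome. Any healing criterion is for the sponsor and DSMB to set; none is proposed here.
4. State whether delayed healing and non-union are recorded as adverse events.

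Make the same change in the DSMB charter. If the interim review has already taken place, document which data the DSMB saw.

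The cost is a few sentences and one listing from data already collected. The study is open-label, single-arm and descriptive, so there is no alpha or unblinding penalty and the sample size does not change. The one practical burden is that V6 films must be scored before the DSMB meets.

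### The interim rule lists only stopping, or continuing with larger defects opened; continuing at up to 3 cm with the larger-defect cohort still closed is not listed

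*Combined protocol and SAP*

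**What the plan says.** The Study Design and Statistical Analysis rows of the Study Synopsis both describe the interim. On timing: "An adaptive interim analysis will be performed when the first 7 Patients will have completed the 6-month follow-up visit". The DSMB then reviews the primary (safety) endpoint and is to "provide one of the following recommendations to the Sponsor: a) to stop the study for unacceptable frequency and severity of adverse events", or, under Study Design, "b) to continue the study up to 25 Patients recruited and to include at least 5 Patients with a longer bone defect" of more than 3 cm and up to 6 cm. Statistical Analysis repeats the pair, with the second option worded "b) to continue the study up to a minimum of 25 Patients recruited and to include at least 5 Patients with a longer" defect.

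Three other rows describe what follows the review:

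- Study Objectives: "Following DSMB interim assessment, at least 5 Patients, of the 25 patients, with a longer bone defect" are to be enrolled.
- Study Population: "After an adaptive interim analysis review by the DSMB, inclusion criteria will be amended", so as to admit defects up to 6 cm.
- Inclusion Criteria: "after interim analysis review by the DSMB, inclusion criteria n. 3 will be modified as follows", again up to 6 cm.

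Separately from the interim, "An independent DSMB will review the safety reports at regular intervals and Serious Adverse Events (SAE) as soon as reported, to protect Patients" in the study.

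**The concern.** The study is first-in-human for a Class III device. It treats defects up to 3 cm first and places a DSMB review before larger defects are treated. That staging works fully only if the review can keep the second stage closed without ending the first. Under the listed options it cannot: the only criterion written is for stopping, and everything else leads to continuing with expansion. A DSMB that sees nothing bad enough to stop, but too little to be comfortable with larger defects, has no listed recommendation that fits. Following the list as written, it would have to stop a study it thinks should go on, or support opening a cohort it thinks should wait.

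**Working it through.** **Text.** The main check is a comparison of every place in the synopsis that describes the interim.

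| Synopsis row | What it provides |
|---|---|
| Study Design | One of two: (a) stop; (b) continue and include at least 5 larger defects |
| Statistical Analysis | The same two; total worded as a minimum of 25 |
| Study Objectives | At least 5 of the 25 with larger defects, after the assessment |
| Study Population | Criteria widened after the review |
| Inclusion Criteria | Criterion 3 changed to up to 6 cm after the review |

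Two decisions are involved: does the study continue, and does the larger-defect cohort open? With two yes/no answers there are three coherent outcomes: stop; continue and open; continue and do not open yet. The synopsis lists the first two. The third appears in no row.

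**How clear can 7 patients be?** The plan gives no error rate or precision for the interim, and the total of 25 was chosen by precedent, so there is no figure of the plan's own to reproduce. The calculation below is context only. The one input from the documents is n = 7. An event means any per-patient adverse outcome the DSMB might count. The synopsis does not say which would weigh most.

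The exact (Clopper-Pearson) two-sided 95% limits for x events in n are the lower limit Beta(0.025; x, n − x + 1) and the upper limit Beta(0.975; x + 1, n − x). For x = 0 the lower limit is 0 and the upper limit reduces to 1 − 0.025^(1/n).

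| Patients with an event | 95% interval |
|---|---|
| 0 of 7 | 0% to 41% (1 − 0.025^(1/7) = 0.410) |
| 1 of 7 | 0.4% to 58% |
| 2 of 7 | 4% to 71% |

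The chance of seeing no event in 7 is (1 − p)^7. The documents give no rate, so p is assumed over a range:

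| Assumed true rate p | (1 − p)^7 |
|---|---|
| 5% | 0.95^7 = 70% |
| 10% | 0.90^7 = 48% |
| 20% | 0.80^7 = 21% |
| 30% | 0.70^7 = 8% |

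One or two affected patients are compatible with rates from very low to above one half, and a clean result is not rare even at a true 20%. An unclear picture is therefore a realistic outcome of this interim.

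**Places available.** If 25 is a ceiling, reserving at least 5 places for larger defects leaves at most 25 − 5 = 20 for defects up to 3 cm. If 25 is a minimum, as Statistical Analysis has it, that limit does not apply.

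**The case against.** The strongest reply is that this argues from silence in a synopsis. The recommendations go to the sponsor and are advisory. Nothing forbids the DSMB from advising something else. It also sees safety reports regularly and serious events promptly, and a charter that was not supplied may contain the missing option. Continuing with expansion carries no date either, so a later opening is not expressly barred. All of this is true, and it limits the weight of the point. It does not supply the option: the synopsis sets out a list from which one item is to be chosen, and it attaches no decision on opening the cohort to the ongoing reviews.

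Second, 7 may understate what the DSMB knows. It is the number who have completed 6 months. No pause in enrolment is stated, so shorter follow-up on further patients may be available. This stands: the intervals above describe the 7 patients and not necessarily all the information at hand.

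Third, a reader might infer from Study Objectives, Study Population and Inclusion Criteria that expansion goes ahead whatever the DSMB says. The documents do not support that. Expansion cannot follow a recommendation to stop, and these rows can fairly be read as shorthand for the second option. They need a conforming edit and are not a separate defect.

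Finally, splitting the decision is partly a design preference. That is fair, and it is why no criterion for opening the cohort is suggested here.

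**Conclusion.** The point holds as a cheap improvement. The two-option list is plain in both rows that set out the DSMB's recommendations, and continuing with the larger-defect cohort still closed is missing from it. The conclusion rests on the text. The intervals show only that an unclear result is plausible with 7 patients, and the event probabilities depend on assumed rates of 5% to 30%.

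A reader might go further and infer that the DSMB is bound to approve expansion, that it is powerless once the interim has passed, or that an upper limit of 41% makes the interim unsafe. The documents support none of these. The advice is not binding, safety review continues, and the DSMB judges frequency and severity, which a per-patient rate does not predict. The remaining uncertainty is whether a charter already covers the case.

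**What to change.** In Study Design and Statistical Analysis, have the DSMB give two separate recommendations: whether the study continues, and whether the cohort with defects of more than 3 cm and up to 6 cm opens. Continuing with the cohort not yet open, and a later re-review, is then permitted. No threshold for opening and no size for a re-review is proposed.

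As a conforming edit, word the expansion in Study Objectives, Study Population and Inclusion Criteria as following a recommendation to open the cohort. If a charter already provides this, cite it in the synopsis.

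The cost is mainly wording, with no new study visits, but patients have already been enrolled, so the change would be made to a study under way. It may require one more DSMB review. If the DSMB holds the cohort, accrual and follow-up come later for the only patients who inform larger defects, and these are part of the primary objective. That delay arises only if the DSMB chooses it. If 25 is a ceiling, the sponsor must keep 5 places free, so no more than 20 patients could have defects up to 3 cm.

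A separate wording point can be settled in the same edit: Study Design treats 25 as an upper limit and Statistical Analysis as a minimum. The two should be reconciled.
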